2.8 Safety analyses

The secondary safety objective and endpoint of this study is as follows:

To evaluate the safety and tolerability of brolucizumab

- Incidence of Ocular and Non-ocular AEs up to week 52

There are no formal safety hypotheses in this study. All safety analyses will be performed using the Safety Set. All listings and tables will be presented by treatment arm.

Safety endpoints are based on the variables from safety assessments which include:

- Extent of exposure
- Adverse events
- Ophthalmic examination and imaging
- Vital signs

Safety summaries (tables, figures) include only data from the on-treatment period with the exception of baseline data which will also be summarized where appropriate (e.g. change from baseline summaries). In addition, a separate summary for death including on treatment and post treatment deaths will be provided. In particular, summary tables for adverse events (AEs) will summarize only on-treatment events, with a start date during the on-treatment period

(treatment-emergent AEs). Separate summary tables will be provided for AEs of study eye, fellow eye and non-ocular AEs.

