5.1.2 AE date imputation

For start date:

- If day missing
 - if month/year(start) gt month/year(first injection) than impute max(date of first injection, mdy(month (start date),1,year(start date)))
else impute mdy(month (start date),1,year(start date))

For end date:

- If complete missing than impute date of last injection+30.
- If day missing
 - if month/year(first injection) gt month/year(end date) than impute mdy(month(end date)+1,1,year(end date))-1)
 - if month/year(first injection) le month/year(end date) le month/year(last injection+30) than impute min(date of last injection+30, mdy(month(end date)+1,1,year(end date))-1)
 - if month/year(end date) gt month/year(last injection+30) than date of last injection+30

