5.1.3 Concomitant medication date imputation

Like AE imputation

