5.4 Statistical models

5.4.1 Primary analysis

1) SAS-Code for **mixed model for repeated measures (MMRM)**:

Estimates for the primary objective ("Mean change in BCVA from baseline to mean of visits at week 40 to week 52 (Visit 11 to 14)") and the secondary objective ("Mean change in BCVA from baseline to mean of visits at week 16 to week 28 (Visit 5 to 8)") in one single model:

```
proc mixed alpha=0.1;
  where fasfl=Y and trteyen=1;
  where 2 le avisitn le 14;
  class subjid trtan avisitn;
  model chg = base age trtan avisitn trtan*avisitn /ddfm=kr;
  repeated avisitn / sub = subjid type = un;
  lsmeans trtan*avisitn /slice = avisitn cl ;
  estimate 'Treatment difference averaged over week 40 to week 52'
    trtan -1 1
    trtan * avisitn
      0 0 0 0 0 0 0 0 -0.25 -0.25 -0.25 -0.25
      0 0 0 0 0 0 0 0 0.25 0.25 0.25 0.25/cl;
  estimate 'Treatment difference averaged over week 16 to week 28'
    trtan -1 1
    trtan * avisitn
      0 0 0 -0.25 -0.25 -0.25 -0.25 0 0 0 0 0 0
      0 0 0 0.25 0.25 0.25 0.25 0 0 0 0 0 0/cl;
run;
```

3) SAS-Code for **logistic regression** model:

- Secondary endpoint: "rate of patients (overall and per treatment arm) with prolonged interval (*intlong*) compared to mean treatment interval in last 24 weeks prior to enrollment"

```
proc logistic descending alpha=0.05;
  where fasfl=Y;
  class trtan;
  model intlong = base age trtan;
run;
```

- Secondary endpoint: "proportions of patients maintained at a q12w interval from baseline / upload to week 52"

```
proc logistic descending alpha=0.05;
  where fasfl=Y;
  class trtan;
  model q12w = base age trtan;
run;
```

where 'maintained at a q12w interval' (q12w = Yes) is defined as DAA = q12w in all visits AND no treatment discontinuation.

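### The end-of-month formula for partial end dates has no year roll-over, so December end dates that reach it ask for month 13

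*SAP*

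**What the plan says.** SAP 5.1.2 gives four rules for adverse event end dates.

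- Whole date missing: "If complete missing than impute date of last injection+30".
- Day missing, end month before the month of first injection (branch 1): "if month/year(first injection) gt month/year(end date) than impute mdy(month(end date)+1,1,year(end date))-1".
- Day missing, end month between the month of first injection and the month of last injection + 30 (branch 2): "than impute min(date of last injection+30, mdy(month(end date)+1,1,year(end date))-1", that is, the earlier of the two dates.
- Day missing, end month later than that (branch 3): "if month/year(end date) gt month/year(last injection+30) than date of last injection+30".

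SAP 5.1.3 consists of a single instruction for concomitant medication dates: "Like AE imputation".

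The section has no separate rule for December, and it does not say in words that the last day of the month is meant. The formula, "mdy(month(end date)+1,1,year(end date))-1", is the only definition given. The SAP's own program code is SAS, as the label in SAP 5.4.1 shows ("SAS-Code for mixed model for repeated measures (MMRM"), and `mdy` is a SAS date function.

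**The concern.** The formula takes the first day of the following month and subtracts one day. That works only if the year also advances when the month passes 12. Here the year is held at the year of the end date, so December leads to month 13.

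Two results would follow. In branch 1 the date is lost, and a record with a known end month looks as if it has no end. In branch 2 the earlier-of-two-dates rule can hide the failure, because the cap of last injection + 30 remains as the only usable value. That value is a plausible date, so someone reading the listing may not notice it.

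This is separate from the cap itself: the date is replaced even where the cap should not have applied. Medications are the more exposed data. SAP 2.4.2 summarises therapies before and after the start of study treatment, and the end date is the natural way to tell a drug stopped earlier from one that continued.

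**Working it through.** The plan states no figure to reproduce here. The check applies the three missing-day branches literally and compares each result with a correct end of month.

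**Inputs**

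- The formula and branches: SAP 5.1.2, carried to medications by 5.1.3.
- First patient recruited in July 2021, with recruitment still open when Amendment 2 was dated 30 November 2022: Protocol, Amendment 2 rationale.
- Treatment from baseline to week 48: Protocol Section 3.
- Assumed: first injections from 1 July 2021 to 31 January 2023, and last injection at week 44 or week 48.
- Assumed SAS behaviour, which the SAP does not describe: `mdy` with an invalid month returns missing, missing minus 1 is missing, and `min` ignores missing arguments.

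**Step 1: the formula.** Write m for the month and y for the year of the end date.

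- m = 1 to 11: `mdy(m+1,1,y) - 1` is the last day of month m. Tested for 2021 to 2024, there were no errors.
- m = 12: `mdy(13,1,y) - 1` is missing. The correct value is 31 December of year y.

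**Step 2: each branch for a December end date**

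| Branch | As written | Correct end of month | Result |
|---|---|---|---|
| 1 | missing | 31 December | always lost |
| 2, last injection + 30 after that December | last injection + 30 | 31 December | too late |
| 2, last injection + 30 in that December | last injection + 30 | last injection + 30 | no error |
| 3 | last injection + 30 | last injection + 30 | formula not used |

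**Step 3: size of the delay in branch 2.** The delay is (last injection + 30) minus 31 December. It is smallest, 1 day, when last injection + 30 is 1 January. It is largest when the first injection is itself on 31 December:

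- last injection at week 48: 48 × 7 + 30 = 366 days
- last injection at week 44: 44 × 7 + 30 = 338 days

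**Step 4: examples, last injection at week 48 (336 days after the first)**

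| First injection | Last injection | Last + 30 | End month | As written | Correct |
|---|---|---|---|---|---|
| 15 Sep 2021 | 17 Aug 2022 | 16 Sep 2022 | Dec 2021 | 16 Sep 2022 | 31 Dec 2021 (259 days earlier) |
| 20 Jan 2022 | 22 Dec 2022 | 21 Jan 2023 | Dec 2021 | missing | 31 Dec 2021 |
| 20 Dec 2021 | 21 Nov 2022 | 21 Dec 2022 | Dec 2022 | 21 Dec 2022 | 21 Dec 2022 |

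**Step 5: can it occur in this trial?** The assumed range holds 184 + 365 + 31 = 580 first-injection dates.

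- Week 48: the window is 366 days, so every first-injection date has at least one December that would be imputed late in branch 2.
- Week 44: this holds for 526 of the 580 dates. The other 54 are 1 to 27 January of 2022 and of 2023, because 27 January + 338 days is 31 December.

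These are counts of calendar dates, not of patients or of affected records.

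**Step 6: what uses the end date.** SAP 2.8 says that the adverse event tables "summarize only on-treatment events, with a start date during the on-treatment period". SAP 2.8.1 counts patients with at least one event. Neither uses the end date, and the SAP lists no summary of event duration.

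**The case against.** The strongest reply is that SAP 5.1.2 is shorthand, not a program. It compares month/year pairs in a form that SAS would not run, and the branch 1 line has an unmatched bracket. The runnable code is set apart in SAP 5.4.1. The intention, the last day of the month, is easy to guess, and a competent programmer may code it correctly without comment. The consequences also rest on SAS behaviour that the documents do not describe. This stands as a limit on the likely harm. It does not repair the text: month 13 is invalid in any language, the section offers no wording to fall back on, and correct code would depart from the plan as written.

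A reader might also infer more than the documents support.

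- *Every December end date is wrong.* It is not. Branch 3 and the rule for a wholly missing date never use the formula, and branch 2 gives the right answer when last injection + 30 falls in the same December.
- *Adverse event incidence is affected.* It is not, because the tables depend on the start date. For adverse events branch 1 is also narrow: recording starts at consent (Protocol 10.1.1), and screening lasts at most 14 days.
- *Medications stopped before treatment will be counted as taken after it began.* SAP 2.4.2 gives no rule that classifies by imputed end date, and none that treats a failed imputation as ongoing. This could happen, but it is not specified.

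**Conclusion.** Wrong as written, minor. A December end date with a missing day that reaches the formula gives month 13. If coded literally in SAS, the result is missing in branch 1. In branch 2 it is last injection + 30 instead of 31 December whenever last injection + 30 falls after that December, which is 1 to 366 days late for a last injection at week 44 or 48. For a patient whose last injection came earlier, the upper limit is the number of days from first to last injection plus 30.

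The number of affected records cannot be derived, because the documents do not say how many partial end dates exist. If these were spread evenly over the year, at most 1/12 = 8.3% would fall in December, and some of those are unaffected. About 50 patients are expected, so the absolute number is likely to be small.

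The effect is confined to adverse event end dates shown in listings and to medication end dates, with possible misplacement in the summary of therapies before and after treatment start. Treatment-emergent adverse event counts, BCVA, treatment intervals and the primary endpoint are not affected.

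**What to change.** In branches 1 and 2 of SAP 5.1.2, replace the formula with the last day of the end month, stating that the year rolls over. In SAS, with m and y the month and year of the end date, one form is `intnx('month', mdy(m,1,y), 0, 'end')`; any equivalent will do. Keep the `min` with last injection + 30 in branch 2. SAP 5.1.3 inherits the correction and needs no change of its own.

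The cost is one line of wording and code. If the derivation programs already exist, list the December end dates with a missing day and confirm that each is imputed as 31 December, or as last injection + 30 where that date is earlier or where branch 3 applies.

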5.1.3 Concomitant medication date imputation

Like AE imputation

5.2 AEs coding/grading

The Medical Dictionary for Regulatory Activities (MedDRA) will be used to code all adverse events (AE) to a system organ class (SOC) and a preferred term (PT). The current version at the time of database closing will be used.

5.3 Laboratory parameters derivations

Not applicable.

5.4 Statistical models

5.4.1 Primary analysis

1) SAS-Code for **mixed model for repeated measures (MMRM)**:

Estimates for the primary objective ("Mean change in BCVA from baseline to mean of visits at week 40 to week 52 (Visit 11 to 14)") and the secondary objective ("Mean change in BCVA from baseline to mean of visits at week 16 to week 28 (Visit 5 to 8)") in one single model:

```
proc mixed alpha=0.1;
  where fasfl=Y and trteyen=1;
  where 2 le avisitn le 14;
  class subjid trtan avisitn;
  model chg = base age trtan avisitn trtan*avisitn /ddfm=kr;
  repeated avisitn / sub = subjid type = un;
  lsmeans trtan*avisitn /slice = avisitn cl ;
  estimate 'Treatment difference averaged over week 40 to week 52'
    trtan -1 1
    trtan * avisitn
      0 0 0 0 0 0 0 0 -0.25 -0.25 -0.25 -0.25
      0 0 0 0 0 0 0 0 0.25 0.25 0.25 0.25/cl;
  estimate 'Treatment difference averaged over week 16 to week 28'
    trtan -1 1
    trtan * avisitn
      0 0 0 -0.25 -0.25 -0.25 -0.25 0 0 0 0 0 0
      0 0 0 0.25 0.25 0.25 0.25 0 0 0 0 0 0/cl;
run;
```

3) SAS-Code for **logistic regression** model:

- Secondary endpoint: "rate of patients (overall and per treatment arm) with prolonged interval (*intlong*) compared to mean treatment interval in last 24 weeks prior to enrollment"

```
proc logistic descending alpha=0.05;
  where fasfl=Y;
  class trtan;
  model intlong = base age trtan;
run;
```

- Secondary endpoint: "proportions of patients maintained at a q12w interval from baseline / upload to week 52"

```
proc logistic descending alpha=0.05;
  where fasfl=Y;
  class trtan;
  model q12w = base age trtan;
run;
```

where 'maintained at a q12w interval' (q12w = Yes) is defined as DAA = q12w in all visits AND no treatment discontinuation.

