12.4.2 Statistical model, hypothesis, and method of analysis

The analysis of the primary endpoint will be performed in a purely descriptive manner and non-inferiority testing will be omitted. To evaluate the outcome in terms of mean change in BCVA from baseline to mean of visits at week 40 through week 52, a two-sided 95% confidence interval for the treatment difference will be derived from a mixed model with repeated measures (MMRM) model with factors treatment arm, baseline BCVA and age. Details will be specified in the respective SAP.

The FAS will be used to analyze the primary endpoint.

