12.5 Analysis of secondary endpoints

12.5.1 Efficacy endpoints

The secondary efficacy objectives and endpoints of this study are listed in [Table 2-1](#).

Secondary endpoints will be analyzed using adequate descriptive statistics.

For continuous variables, summary statistics will generally include: n, mean, standard deviation, median, minimum and maximum. Treatment group comparisons may include confidence intervals and group differences together with the respective confidence intervals.

The secondary endpoint "Mean change in BCVA from baseline to mean of visits week 16 to week 28" will be analyzed analogous to the primary endpoint analysis.

For categorical variables, these will generally include: n and percentage in each category.

Rates and percentages will be presented for binary variables.

For the endpoints "rate of patients (overall and per group) with prolonged interval compared to mean treatment interval in last -24 weeks prior to enrollment" and "proportions of patients maintained at a q12w interval at week 52" a logistic regression model will be fitted.

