2.5.2 Statistical hypothesis, model, and method of analysis

The analysis of the primary endpoint will be performed in a purely descriptive manner and non-inferiority testing will be omitted. To evaluate the outcome in terms of mean change in BCVA from baseline to mean of visits at week 40 through week 52, a two-sided 95% confidence interval for the treatment difference will be derived from a mixed model with repeated measures (MMRM) model with factors treatment arm, baseline BCVA and age. An unstructured

covariance structure shared across treatment arms was used to model the within-patient errors. Programming details are specified in section 5.4.

The FAS will be used to analyze the primary endpoint.

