2.7.2 Statistical hypothesis, model, and method of analysis

Secondary endpoints will be analyzed using adequate descriptive statistics, if not otherwise specified. Details on planned analyses are listed in the table below.

Table 2 Endpoints and statistical method

Endpoints for secondary objectives	Statistical method
1.Treatment interval	
1.1. Mean treatment interval (overall as well as per study group comparing treatment intervals from week 8 to week 52 in the study vs. 24 weeks to baseline prior to enrollment)	Descriptive analysis of injection intervals (weeks): Summary statistics (n,mean, SD, min, median, max) for - Mean treatment interval from week 8 to week 52 - Mean treatment interval within 24 weeks prior to baseline. - Last treatment interval under observation Box Plot for “last treatment interval under observation”. Stacked Bar Chart for patients on q8w and q12w by visit (last documented DAA).

1.2. Rate of patients (overall and per group) with prolonged interval compared to mean treatment interval in last 24 weeks to baseline prior to enrollment

- **Frequencies and percentages (n(%))** for total FAS and both treatment arms.

- **Logistic regression model**

Dependent variable: interval prolongation* (Y/N)

Factors:

- treatment arm
- baseline BCVA
- age

Odds-ratio, 95% CI and p-value.

Estimates for , non-loading arm, loading arm and difference (non-loading – loading).

* Prolongation is calculated by comparing the “mean treatment interval in last 24 weeks prior to first brolucizumab injection” (defined in section 2.3.2) with the time interval between the last two brolucizumab injections. Patients with only one injection in treatment period are calculated as non-responders (no interval prolongation).

2. Maintenance of q12w intervals

2.1. Comparison of proportions of patients maintained at a q12w interval at week 52 between the two arms

- **Frequencies and percentages (n(%))** for total FAS and both treatment arms.

- **Logistic regression model**

Dependent variable: “q12w” (Yes/No): “DAA maintained at q12w from baseline / upload to week 52”

Factors:

- treatment arm
- baseline BCVA
- age

Odds-ratio with 95% CI and p-value.

Patients who discontinued treatment prior to week 52 are calculated as non-responders.

2.2. Distributions of patients at q8w/q12w intervals from baseline to week 52

Descriptive statistics for treatment regimens:
Frequencies and percentages (n (%)) by visit

3. Functional Outcomes

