3.1. Average change in BCVA from baseline to week 52

Descriptive statistics for course and change in BCVA:
Summary statistics (n,mean, SD, min, median, max) for BCVA in the study eye by visit.

3.2. Proportion of patients with BCVA improvements of ≥ 5 , ≥ 10 , and ≥ 15 letters from baseline to week 52
3.3. Proportions of BCVA ≥ 69 letters at week 52

3.4. Mean change in BCVA from baseline to mean of visits week 16 to week 28

Descriptive statistics (**rates and percentages**) for proportion of patients with:

- Gain* in BCVA of ≥ 5 ETDRS letters
- Gain* in BCVA of ≥ 10 ETDRS letters
- Gain* in BCVA of ≥ 15 ETDRS letters

*from baseline to week 52

Mixed model for repeated measures (MMRM)

Factors:

- treatment arm
- baseline BCVA
- age

Least square means with SE and 90% CI.

4. Anatomical outcomes

4.1. Change from baseline in CST as assessed by SD-OCT per visit up to week 52
4.2. Absence of IRF, SRF, and sub-RPE fluid as assessed by SD-OCT per visit up to week 52
4.3. Presence of active CNV leakage as assessed by fluorescein angiography at week 52

Descriptive analysis of anatomical outcomes:
Frequencies and percentages, **n (%)**, by visit

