2.14 Interim analysis

There is no interim analysis planned.

3 Sample size calculation

Due to feasibility reasons, resulting in a substantial delay in recruitment, as described above, with Amendment 2 the recruitment will be prematurely discontinued. A final number of approximately 50 patients is expected to be recruited by the time of approval of the amendment.

As a consequence, all analyses will be performed and interpreted in a purely descriptive manner.

Based on an expected sample size of 25 patients per group, and an assumed common standard deviation of 13 letters, a precision in terms of the width of the respective 95% confidence interval for the difference in change from baseline of the visual acuity of +/- 7,21 can be achieved. Taking into account the current number of patients of (for 23 patients per group), the precision in terms of the half width of the 95% confidence interval would be 7,51.

4 Change to protocol specified analyses

The wording of secondary objective 2) was slightly changed to: "Comparison of proportions of patients maintained at a q12w interval **from baseline / upload to week 52**" instead of per protocol: "Comparison of proportions of patients maintained at a q12w interval **at week 52**".

5 Appendix

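### The SAP promises a 95% interval for the primary BCVA difference, but its only MMRM code states alpha=0.1 and cannot also serve the 90% level set for week 16–28

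*SAP*

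**What the plan says.** Protocol 12.4.2 states that "a two-sided 95% confidence interval for the treatment difference will be derived from a mixed model with repeated measures (MMRM) model". SAP 2.5.2 repeats it ("a two-sided 95% confidence interval for the treatment difference will be derived from a mixed model with repeated measures") and sends the reader to SAP 5.4 for the programming.

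In SAP 5.4.1 a single MMRM call yields both the week 40–52 and the week 16–28 contrasts. It begins "proc mixed alpha=0.1". The LSMEANS statement and both ESTIMATE statements request confidence limits but carry no level of their own. The two logistic models in the same section are coded with "proc logistic descending alpha=0.05", which agrees with SAP Table 2 for the prolonged-interval endpoint ("Odds-ratio, 95% CI and p-value").

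For the week 16–28 endpoint, SAP Table 2 item 3.4 asks for "Least square means with SE and 90% CI". Protocol 12.5.1 says that this endpoint "will be analyzed analogous to the primary endpoint analysis" and gives no level. SAP section 4, which lists departures from the protocol analyses, has one entry: "The wording of secondary objective 2) was slightly changed to". It concerns the q12w endpoint and does not mention a confidence level.

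**The concern.** The SAP text and the SAP code give different levels for the same primary interval, and the text names the code as its implementation. A programmer who follows SAP 2.5.2 and one who follows SAP 5.4.1 could produce different primary tables, each with a SAP section to cite.

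Since Amendment 2 the trial is descriptive and non-inferiority testing is dropped. The confidence interval for the difference is therefore the planned expression of uncertainty for the primary endpoint, and SAP 2.5.4 plans no sensitivity analysis beside it. If a 90% interval were reported where the protocol and SAP lead readers to expect 95%, the precision of a small trial would look better than planned.

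**Working it through.** **1. Inputs.** 25 per arm expected, 23 per arm as the alternative, and a common SD of 13 letters (Protocol 12.8.1; SAP section 3). Level 95% for the primary (Protocol 12.4.2; SAP 2.5.2). Level stated in the MMRM code: alpha=0.1, which is 90% (SAP 5.4.1). Level for week 16–28: 90% (SAP Table 2 item 3.4).

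**2. Reproduce the plan's own figures.** Half-width = z × SD × √(2/n).

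- SE at 25 per arm: 13 × √(2/25) = 3.677. At 23 per arm: 13 × √(2/23) = 3.834.
- 95%, normal quantile: 1.960 × 3.677 = 7.21 and 1.960 × 3.834 = 7.51.

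Both match the stated 7.21 and 7.51. Solved backwards, those figures imply levels of 95.01% and 94.99%, so the plan's precision statement is a 95% statement.

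**3. The same figures at the level in the code.**

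| Per arm | Quantile | 95% half-width | 90% half-width | Ratio |
|---|---|---|---|---|
| 25 | normal (1.960; 1.645) | 7.21 | 6.05 | 0.839 |
| 23 | normal (1.960; 1.645) | 7.51 | 6.31 | 0.839 |
| 25 | t, df 48 (2.011; 1.677) | 7.39 | 6.17 | 0.834 |
| 23 | t, df 44 (2.015; 1.680) | 7.73 | 6.44 | 0.834 |

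The narrowing is 16 to 17%, or 1.2 to 1.3 letters, with either quantile. For df from 30 to 48 the t ratio stays between 0.831 and 0.834.

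**4. Can the call satisfy both SAP statements?** The documents do not say whether an alpha on the procedure line governs the limits from LSMEANS and ESTIMATE, so both cases are taken.

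- *It governs.* All limits are 90%. Table 2 item 3.4 is met; SAP 2.5.2 and Protocol 12.4.2 are not.
- *It does not govern.* All limits take one software default. If that default is 95% (an assumption, since the documents do not give it), SAP 2.5.2 is met and item 3.4 is not.

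No statement in the call has its own level, so the limits share a common level in both cases. The call cannot return 95% for the primary difference and 90% for the week 16–28 means.

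**5. Was a change of level declared?** No. SAP section 4 does not mention one, and both logistic calls use 0.05, so the MMRM call is the only model code at a different level.

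**The case against.** The strongest reply is that harm to the primary interval is not shown. The prose is consistent at 95%, no sentence in either document says the primary interval is 90%, and whether the procedure-line option reaches the contrast limits is a software matter that the documents leave open. This stands as a limit on the claim: the half-widths in the 90% column apply only in the first case of step 4, and it would be wrong to assert that the primary interval will be 90%. It does not remove the conflict, which is present in both cases. Nor do the documents say that text overrides code; SAP 2.5.2 itself refers to the code.

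A second reply is that item 3.4 concerns least square means for a secondary endpoint, while SAP 2.5.2 concerns the primary difference, and a plan may use different levels for different quantities. That is fair. Protocol 12.5.1 gives no level, and 95% for week 16–28 follows only if an analogous analysis is taken to include the level. A 90% level there is open to the sponsor, but then it has to be coded separately.

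A third reply is that little depends on it: there is no margin, test or sample size tied to the level, the point estimate and standard error do not change, and either interval can be computed from the same fit. All of this is correct and bounds the consequence. The level of the primary interval should still be settled by the plan and not by the programmer's choice of section.

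**Conclusion.** The concern holds. As written, the MMRM code in SAP 5.4.1 cannot meet both SAP 2.5.2 and Table 2 item 3.4. This follows from the documents alone and does not depend on how the software treats the option.

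The size of the effect is conditional. If alpha=0.1 governs the ESTIMATE limits, the primary interval is 16 to 17% narrower than planned and its nominal non-coverage is 10% instead of 5%. If it does not, and the default is 95%, the primary interval is as planned and the only mismatch is the 90% in item 3.4. The half-widths rest on the plan's SD of 13 and equal arms; the MMRM interval, adjusted for baseline BCVA and age, will differ from them at either level. The matter should be corrected before the primary table is produced, because this interval is the main planned statement of uncertainty.

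**What to change.** - Remove alpha=0.1 from the procedure line. State alpha=0.05 explicitly on both ESTIMATE statements and on LSMEANS.
- Change Table 2 item 3.4 to 95%. If 90% is intended for week 16–28, set it only on the statements that produce that output, and declare and justify it in SAP section 4.
- While editing, decide whether item 3.4 means arm-level means averaged over week 16–28. LSMEANS is coded by visit and the ESTIMATE gives only the between-arm difference, so averaged arm means would need their own statements whatever the level.

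The cost is a few code options and one figure in Table 2. No new data, visits or model are needed, and the reported interval may be wider only in the sense that the protocol already plans for.

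This settles the level only. The week 40–52 ESTIMATE prints 12 coefficients per arm for 13 visits (2 to 14), which is a separate point to check against the source document.
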